5 INVESTIGATIONAL PLAN

5.1 DESCRIPTION OF THE OVERALL STUDY DESIGN AND PLAN

5.1.1 Study Design

This will be a Phase III, modified double-blind, randomized, parallel-group, active-controlled, multi-center study to evaluate immune non-inferiority of MenACYW conjugate vaccine versus Menactra® and describe the safety and additional immunogenicity of the study vaccines in children (2-9 years of age), adolescents (10-17 years of age) and adults (18-55 years of age) in Japan. Approximately 360 healthy children, adolescents and adults will be stratified and randomly assigned in a 1:1 ratio to the following groups:

- Group 1 (investigational): MenACYW conjugate vaccine (180 subjects)
- Group 2 (control): Menactra® (180 subjects)

All subjects will provide blood samples for immunogenicity assessment at baseline (pre-vaccination) and at 30 days post-vaccination.

Solicited injection site and systemic reactions will be collected for 7 days after vaccination, unsolicited AEs will be collected from Visit 1 (D0) to Visit 2 (D30 [+14 days]), and SAEs will be collected from signing of the informed consent at D0 through D30 (+14 days) after vaccination.

5.1.2 Justification of the Study Design

This trial is part of the ongoing development program that focuses on demonstrating that MenACYW conjugate vaccine is non-inferior to the licensed quadrivalent meningococcal conjugate vaccine in direct comparison trials. This is a study that will be conducted as part of the Phase III development of MenACYW conjugate vaccine in which the vaccine candidate will be evaluated in children, adolescents, and adults 2 to 55 years of age in Japan.

This trial is designed to evaluate the immune non-inferiority of MenACYW conjugate vaccine versus Menactra®, and will describe the safety and immunogenicity of MenACYW conjugate vaccine and Menactra® in children, adolescents, and adults 2 to 55 years of age in Japan.

This trial will be conducted in a modified double-blind method, in which only designated staff members at each study site will know which vaccine has been administered to the subjects. The subjects and the Investigator in charge of the safety assessment will be blinded in order to decrease the potential bias in safety assessments. The vaccines are prepared by the unblinded site staff member (a designated administrator such as a subinvestigator, a nurse, or a designated pharmacist) and administered by the administrator without the presence of any other site staff members who may be an assessor for safety in subsequent visits. The subjects and subjects' parents / legally acceptable representatives will also remain blinded to study product. Furthermore,

the Sponsor and laboratory personnel performing the serology testing will also remain blinded to treatment assignments throughout the trial until database lock.

5.1.3 Study Plan

A schedule of assessments and study vaccinations is provided in the Table of Study Procedures.

Vaccination

All subjects will receive a single IM dose of either MenACYW conjugate vaccine or Menactra® on D0.

Blood sampling

All subjects will provide a pre-vaccination blood sample at Visit 1 D0 and a post-vaccination sample at Visit 2 (D30 [+14 days] after the vaccination at Visit 1).

Collection of safety data

- All subjects will be observed for 30 minutes after vaccination, and any unsolicited systemic AEs occurring during that time will be recorded as immediate unsolicited systemic AEs in the case report form (CRF).
- The subject or the subject's parent / legally acceptable representative will record information in a diary card about solicited reactions from D0 to D07 after vaccination and unsolicited AEs from Visit 1 (D0) to Visit 2 (D30 [+14 days]). SAEs will be reported throughout the duration of the study from the signing of the ICF or the assent form.
- In addition, the subject or subject's parent / legally acceptable representative will be asked to notify the site immediately about any potential SAEs at any time during the study.
- Study site staff will contact the subject or the subject's parent / legally acceptable representative by telephone on D8 (+2 days) to identify the occurrence of any SAE not yet reported and to remind them to complete the diary card up to Visit 2 and to bring it back at Visit 2.
- The completed diary card will be reviewed with the subject and/or the subject's parent / legally acceptable representative at Visit 2.

5.1.4 Visit Procedures

Medical procedures (examinations, injections, etc.) must be conducted by appropriately licensed or credentialed study site staff working within the scope of their license/credentials.

Visit 1 (D0): Inclusion, Randomization, Blood Sample, and Vaccination

1. Give the subject and/or the subject's parent / legally acceptable representative information about the study, answer any questions, obtain written informed consent and assent (as applicable) and give the subject or subject's parent / legally acceptable representative a signed copy of the ICF and a signed copy of the assent form (as applicable).

- Subjects 2 to 6 years of age: ICF signed by the subject's parent / legally acceptable representative
- Subjects 7 to 19 years of age: assent form signed by the subject and ICF signed by the subject's parent / legally acceptable representative
- Subjects 20 to 55 years of age: ICF signed by the subject

2. Check inclusion and exclusion criteria for eligibility (see [Section 5.2.4](#) and [Section 5.2.5](#), respectively).
3. Collect relevant demographic information.
4. Perform urine pregnancy test (if applicable).
5. Obtain verbal medical history about the subject.
6. Conduct a history-directed physical examination, including temperature (preferably axillary temperature). A physical examination conducted during the same day as part of routine clinical care may be used for this purpose.
7. Contact the interactive response technology (IRT) for subject identification number and vaccine dose number (see [Section 6.5](#) for instructions).
8. Obtain the first blood sample (5 milliliter [mL]) (see [Section 7](#) for detailed instructions regarding the handling of blood samples). If attempts to obtain the first blood draw are unsuccessful (no more than 3 attempts), then Visit 1 can be rescheduled to a later date at which point informed consent and inclusion/exclusion criteria must be re-validated. If the first blood draw cannot be obtained, the subject will be withdrawn from the study without being vaccinated.
9. Administer the appropriate study vaccine to the subject in the deltoid muscle. The vaccine must be administered on the side opposite to that of the blood sampling.
Note: The study product is prepared by an unblinded study site staff (a designated administrator such as a Sub-investigator or nurse, or a designated pharmacist) and administered by the administrator without the presence of any other study site staffs who may be an assessor for safety in subsequent visits. The subjects and subjects' parents / legally acceptable representatives are blinded with eye mask or other appropriate methods during administration.
10. Observe the subject for 30 minutes, and record any AE in the source document.
11. Give the subject or the subject's parent / legally acceptable representative a diary card, a thermometer, and a ruler, and go over the instructions for their use.
12. Remind the subject or the subject's parent / legally acceptable representative to expect a telephone call 8 days (+2 days) after Visit 1 and to bring back the diary card when they return for Visit 2 at a specified date and time.
13. Remind the subject or the subject's parent / legally acceptable representative to notify the site in case of an SAE.
14. Complete the relevant CRF pages for this visit.

Telephone Call 1 (D8 [+2 days] after Visit 1)

Note: If D8 falls on a weekend or a holiday, the telephone call may be made on the following business day. If the subject or the subject's parent / legally acceptable representative is not available, the study site staff should document the attempts to make contact.

1. Record relevant information concerning the subject's health status on the telephone contact form. If an SAE occurred, follow the instructions in [Section 10](#) for reporting it.
2. Remind the subject or the subject's parent / legally acceptable representative to do the following:
 - Complete the D0 to D7 pages of the diary card.
 - Complete the remaining pages of the diary card, and bring them to Visit 2.
 - Notify the site in case of an SAE.

Visit 2 (D30 [+14 days] after Visit 1): Collection of Safety Information and Blood Sample

1. Review the pages of the diary card with the subject or the subject's parent / legally acceptable representative, including any AEs, medications, or therapy that occurred since vaccination.
2. Review the temporary contraindications for blood sampling (see [Section 5.2.8](#)).
3. Obtain the second blood sample (see [Section 7](#) for detailed instructions regarding the handling of blood samples).
4. Complete the termination record of the CRF.
5. If the subject does not return for Visit 2, and the diary card is not received at the site, study site staffs will contact the subject or the subject's parent / legally acceptable representative by telephone. During the telephone call, the subject or the subject's parent / legally acceptable representative will be reminded to return the diary card to the study site. Telephone calls will be documented on the telephone/interview record. If the study site staffs are unable to contact the subject or the subject's parent / legally acceptable representative with 3 attempts, the study site staffs will follow instructions given in [Section 5.2.11](#).
6. Contact the IRT to inform the subject's status.

Follow-up of subjects with Related AEs or with AEs That Led to Study Discontinuation:

Unless a subject or subject's parent / legally acceptable representative refuses further contact, each subject who experiences an AE (whether serious or non-serious) during the study must be followed until the condition resolves, becomes stable, or becomes chronic (even after the end of the subject's participation in the study) if either of the following is true:

- The AE is considered by the Investigator to be related to the product administered.
- The AE caused the discontinuation of the subject from the study.

5.1.5 Planned Study Calendar

The following dates are approximate. The actual dates may differ as, for example, the study will not start until all the appropriate regulatory and ethical approvals have been obtained.

Planned study period - FVFS (first visit, first subject) to LCLS (last contact, last subject): 22 May 2020 to 16 December 2020

Planned inclusion period - FVFS to FVLS (first visit, last subject): 22 May 2020 to 11 November 2020

Planned vaccination period: 22 May 2020 to 11 November 2020

Planned end of study (LCLS): 16 December 2020

Planned date of final clinical study report: 26 Jun 2021

5.2 ENROLLMENT AND RETENTION OF STUDY POPULATION

5.2.1 Recruitment Procedures

Before the start of the study, the Investigator and/or study site staff may contact the subjects or the subjects' parents / legally acceptable representatives of an appropriate pool of potential subjects and invite them to participate in the study. The site will ensure that any advertisements used to recruit subjects (e.g., letters, pamphlets, and posters) are submitted to Sponsor for review prior to submission to the IRB/IEC for approval.

In addition, a potential subject who comes to a study site for a routine visit may be invited to enroll in the study, or a parent who brings a child to the study site for a routine visit may be invited to enroll the child in the study, if eligible. Subjects may also be recruited from the general population.

5.2.2 Informed Consent Procedures

The Investigator (according to applicable regulatory requirements), or a person designated by the Investigator and under the Investigator's responsibility, should fully inform the subject and/or subject's parent / legally acceptable representative of all pertinent aspects of the clinical study including the written information giving approval / favorable opinion by the ethics committee (IRB/IEC). All participants should be informed to the fullest extent possible about the study, in language and terms they are able to understand.

Prior to a subject's participation in the clinical study, the written ICF (and assent form) should be signed, name filled in, and personally dated by the subject and/or by subject's parent / legally acceptable representative, and by the person who conducted the informed consent discussion. A copy of the signed and dated written ICF (and assent form) will be provided to the subject or subject's parent / legally acceptable representative.

The ICF (and assent form) used by the Investigator for obtaining the informed consent of the subject or subject's parent / legally acceptable representative must be reviewed and approved by the Sponsor prior to submission to the appropriate ethics committee (IRB/IEC) for approval / favorable opinion.

The written ICF and any other written information to be provided to subjects or subjects' parents / legally acceptable representatives should be revised whenever important new information becomes available that may be relevant to the consent of the subject or subject's parent / legally acceptable representative. Any revised written ICF and assent form, and written information should receive the IRB/IEC's approval / favorable opinion in advance of use. The subject and/or subject's parent / legally acceptable representative should be informed in a timely manner if new information becomes available that may be relevant to the willingness of the subject or subject's parent / legally acceptable representative to continue participation in the study. The communication of this information should be documented. In case of study suspension due to safety concerns, subjects and/or subjects' parents / legally acceptable representatives will be informed of this study suspension and the reason for it. Once it is confirmed that it is safe for the study to continue, subjects and/or subjects' parents / legally acceptable representatives will be asked to confirm their agreement to continue the study.

5.2.3 Screening Criteria

There are no screening criteria other than the inclusion and exclusion criteria.

5.2.4 Inclusion Criteria

An individual must fulfill all of the following criteria to be eligible for study enrollment:

- I 01. Aged 2 to 55 years on the day of inclusion
- I 02. Informed consent form has been signed and dated by the subjects or subjects' parents / legally acceptable representatives as applicable
In addition:
Subjects 7 to 19 years will provide written assent
- I 03. Subjects (and subjects' parents / legally acceptable representatives for the 2 to 19 years age groups) are able to attend all scheduled visits and to comply with all study procedures

5.2.5 Exclusion Criteria

An individual fulfilling any of the following criteria is to be excluded from study enrollment:

- E 01. Subject is pregnant, or lactating, or of childbearing potential (to be considered of non-childbearing potential, a female must be pre-menarche or post-menopausal for at least

1 year, surgically sterile, or using an effective method of contraception¹ or abstinence from at least 4 weeks prior to vaccination until at least 4 weeks after vaccination)

- E 02. Participation in the 4 weeks preceding the study vaccination or planned participation during the present study period in another clinical study investigating a vaccine, drug, medical device, or medical procedure
- E 03. Receipt of any vaccine in the 4 weeks preceding the study vaccination or planned receipt of any vaccine prior to Visit 2 except for influenza vaccination, which may be received at least 2 weeks before or after the study investigational vaccines. This exception includes monovalent pandemic influenza vaccines and multivalent influenza vaccines
- E 04. Previous vaccination against meningococcal disease with either the study vaccine or another vaccine (i.e., mono- or polyvalent, polysaccharide, or conjugate meningococcal vaccine containing serogroups A, C, Y, or W; or meningococcal B vaccine)
- E 05. Receipt of immune globulins, blood or blood-derived products in the past 3 months
- E 06. Known or suspected congenital or acquired immunodeficiency; or receipt of immunosuppressive therapy, such as anti-cancer chemotherapy or radiation therapy, within the preceding 6 months; or long-term systemic corticosteroid therapy (prednisone or equivalent for more than 2 consecutive weeks within the past 3 months)
- E 07. History of meningococcal infection, confirmed either clinically, serologically, or microbiologically
- E 08. At high risk for meningococcal infection during the study (specifically, but not limited to, subjects with persistent complement deficiency, with anatomic or functional asplenia, or subjects traveling to countries with high endemic or epidemic disease)
- E 09. Known systemic hypersensitivity to any of the vaccine components, or history of a life-threatening reaction to the vaccines used in the study or to a vaccine containing any of the same substances
- E 10. Laboratory confirmed / self-reported thrombocytopenia, contraindicating intramuscular vaccination in the Investigator's judgment
- E 11. Bleeding disorder, or receipt of anticoagulants in the 3 weeks preceding inclusion, contraindicating intramuscular vaccination in the Investigator's judgement
- E 12. History of GBS
- E 13. History of convulsions

¹ Effective methods of contraception include oral contraception (pill), intrauterine device, or condoms used with spermicide.

- E 14. History of an Arthus-like reaction after vaccination with a tetanus toxoid-containing vaccine and a diphtheria toxoid-containing vaccine within 10 years of the proposed study vaccination
- E 15. Deprived of freedom by an administrative or court order, or in an emergency setting, or hospitalized involuntarily
- E 16. Current alcohol abuse or drug addiction
- E 17. Chronic illness that, in the opinion of the Investigator, is at a stage where it might interfere with study conduct or completion
- E 18. Moderate or severe acute illness/infection (according to Investigator judgment) or febrile illness (temperature $\geq 99.5^{\circ}\text{F}$ or $\geq 37.5^{\circ}\text{C}$) on the day of vaccination. A prospective subject should not be included in the study until the condition has resolved or the febrile event has subsided
- E 19. Receipt of oral or injectable antibiotic therapy within 72 hours prior to the first blood draw
- E 20. Identified as an Investigator or employee of the Investigator or study center with direct involvement in the proposed study, or identified as an immediate family member (i.e., parent, spouse, natural or adopted child) of the Investigator or employee with direct involvement in the proposed study

If the subject has a primary physician who is not the Investigator, the site should contact this physician with the consent of the subject or subject's parent / legally acceptable representative to inform him/her of the subject's participation in the study. In addition, the site should ask this primary physician to verify exclusion criteria relating to previous therapies, such as receipt of blood products or previous vaccines.

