1.3.2 Potential Risks to Subjects

Like other vaccines, vaccination with MenACYW conjugate vaccine or Menactra® may cause injection site reactions such as pain, swelling, induration, and erythema, or certain systemic events such as fever, headache, malaise, or myalgia.

Other common reactions after Menactra® in the studied age group include injection site induration, fatigue, arthralgia, appetite lost, and diarrhea.

There may be a rare possibility of an allergic reaction which could be severe. Prior to any vaccine injection, all known precautions should be taken to prevent hypersensitivity reactions. This includes a review of the subject's prior vaccination history with respect to possible hypersensitivity to the vaccine or similar vaccines. Epinephrine injection (1:1000) and other appropriate agents used for the control of immediate allergic reactions must be available to treat unexpected reactions (e.g., anaphylaxis).

There may also be a risk of febrile convulsion in some children who experience high fever.

There may be other risks for MenACYW conjugate vaccine which are not yet known.

[figure not shown]
The following additional adverse events have been very rarely reported during post-approval use of Menactra®: Guillain-Barré syndrome (GBS), transverse myelitis, acute disseminated encephalomyelitis, vasovagal syncope, facial palsy, dizziness, paraesthesia, convulsion, and hypersensitivity reactions such as anaphylactic / anaphylactoid reaction, wheezing, difficulty breathing, upper airway swelling, urticaria, erythema, pruritus, and hypotension. Because these events were reported voluntarily from a population of uncertain size, it is not possible to reliably estimate their frequency or to establish a causal relationship to Menactra® exposure.

GBS has been reported mostly in persons aged 11 to 19 years who had symptom onset within 6 weeks of administration of Menactra® (29). A retrospective cohort study carried out in the USA using healthcare claims data found no evidence of increased GBS risk following Menactra® vaccination. The study was able to exclude all but relatively small incremental risks (30).

A review by the Institute of Medicine (IOM) found inadequate evidence to accept or reject a causal relationship between tetanus toxoid-containing vaccines and GBS (31). The IOM found

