5.2.6 Medical History

Prior to enrollment, subjects will be assessed for pre-existing conditions and illnesses, both past and ongoing. Any such conditions will be documented in the source document. Significant (clinically relevant) medical history (reported as diagnosis) including conditions/illnesses for which the subject is or has been followed by a physician or conditions/illnesses that could resume during the course of the study or lead to an SAE or to a repetitive outpatient care will be collected in the case report book (CRB). The significant medical history section of the CRB contains a core list of body systems and disorders that could be used to prompt comprehensive reporting, as well as space for the reporting of specific conditions and illnesses.

For each condition, the data collected will be limited to:

- Diagnosis (this is preferable to reporting signs and symptoms)
- Presence or absence of the condition at enrollment

The reporting of signs and symptoms in lieu of a diagnosis is strongly discouraged.

Dates, medications, and body systems are not to be recorded, and the information collected will not be coded. Its purpose is to assist in the later interpretation of safety data collected during the study.

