13.4 MONITORING, AUDITING, AND ARCHIVING

13.4.1 Monitoring

Before the start of the study (i.e., before the inclusion of the first subject in the first center), the Investigators and the Sponsor's staff or a representative will meet at the site-initiation visit to discuss the study protocol and the detailed study procedures. Emphasis will be placed on inclusion and exclusion criteria, visit timing, safety procedures, informed consent procedures, SAE reporting procedures, CRB completion, and the handling of samples and products. The Sponsor's monitoring staff or a representative will ensure and document that all material to be used during the study has been received at the site; and that the study investigator team and local Sponsor / delegate staff have been properly informed about the study, GCP and regulatory requirements, and the Sponsor's procedures. Specific training sessions for the study investigator team and the Sponsor's monitoring staff on these topics may be performed as necessary, and should be documented.

The following instruction manuals will be provided: the CRF Completion Instructions for entering data into the CRB, and the guidelines for detailed study procedures such as the product management, sample-handling procedures and IRT operation manuals.

After the start of the study, the Sponsor's staff or a representative will be in regular contact with the investigational team through telephone calls and regular follow-up visits. The Investigator or delegate must be available for these visits, and must allow the Sponsor / delegate staff direct access to subject medical files and CRBs. During these visits, the Sponsor / delegate staff will:

- Evaluate the quality of the study progress (adherence to protocol and any study-specific guidelines, quality of data collection and document completion, signature of consent forms, occurrence of SAEs, sample and product management, cold-chain monitoring, archiving).
- Source-verify completed CRBs and any corresponding answered queries.
- Determine the number of complete or ongoing issues identified at monitoring visits (e.g., protocol deviations, SAEs). Any identified problems will be discussed with the Investigator, and corrective or preventive actions will be determined, as appropriate.

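### Exclusion E 14 joins the two toxoid vaccine histories with *and* where *or* was probably meant, so read literally it misses an Arthus-like reaction after a single-toxoid vaccine (minor)

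*Protocol*

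**What the plan says.** E 14 in Protocol section 5.2.5 excludes a person with "History of an Arthus-like reaction after vaccination with a tetanus toxoid-containing vaccine and a diphtheria toxoid-containing vaccine within 10 years" before the study vaccination. The Synopsis has the same wording. Fulfilling any one exclusion criterion is enough to bar enrollment, so the wording inside E 14 decides whether E 14 applies.

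The nearest other criterion is E 09. Its first part covers "Known systemic hypersensitivity to any of the vaccine components". Its second part covers a "history of a life-threatening reaction to the vaccines used in the study or to a vaccine containing any of the same substances". No other criterion names Arthus-like reactions.

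Section 6.1.1.1 gives tetanus toxoid as the carrier in MenACYW, and section 6.1.2.1 gives diphtheria toxoid as the carrier in Menactra. Section 6.5 randomizes 1:1, stratified only by age. Section 1.3.2 says that Arthus reactions, though rare, can follow tetanus toxoid-containing vaccines, and that none was reported with MenACYW in the completed trials.

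**The concern.** No subject receives both carriers. For a person assigned to MenACYW, a previous Arthus-like reaction to tetanus toxoid is the relevant history; for a person assigned to Menactra, it would be a reaction to diphtheria toxoid. Because assignment is not known at screening, the criterion has to exclude a reaction to either. As worded, it asks for a reaction linked to both.

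Two things are at stake, both small. The first is safety: under the literal reading, E 14 does not stop a person who reacted to one toxoid from being assigned the vaccine that carries it. The second is consistency: two sites could decide differently on the same history. The same ambiguity carries into the Per-Protocol Analysis Set, because Protocol section 12.2.3 and SAP Table 4 remove anyone who met an exclusion criterion.

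**Working it through.** The plan gives no figure on this point, so the check is mainly one of logic. Take a local Arthus-like reaction within the 10-year window that was neither systemic nor life-threatening, and apply each reading.

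| Previous reaction followed | E 14 with *and*, literal | E 14 with *or* | E 09 |
|---|---|---|---|
| Tetanus-only vaccine | not met | met | not met |
| Diphtheria-only vaccine | not met | met | not met |
| Combined tetanus-diphtheria vaccine | met | met | not met |
| One vaccine of each type | met | met | not met |

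The readings differ only in the first two rows. E 09 does not fill those rows. Its first part needs systemic hypersensitivity. Its second part does reach vaccines that share a substance with the study vaccines, but only for life-threatening reactions.

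**How many people this could affect.** The documents give no frequency of previous Arthus-like reactions and do not say how often single-toxoid vaccines are used, so the number cannot be estimated. For scale, one subject is 1/360 = 0.28% of the planned total.

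**What the documents do allow.** Section 1.2.2 reports approximately 7613 MenACYW recipients in 12 completed trials (different formulations). Section 1.3.2 reports no Arthus reaction in completed trials. If both refer to the same trials, the data are 0 events in 7613:

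- Two-sided 95% Clopper-Pearson upper limit: 1 − 0.025^(1/7613) = 0.000484, or 0.048%.
- Expected reactions at that limit among the 180 planned Group 1 subjects: 180 × 0.000484 = 0.087.
- One-sided 95% upper limit: 1 − 0.05^(1/7613) = 0.000393, or 0.039%; 180 × 0.000393 = 0.071.

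These limits describe new reactions in vaccinees in general. They are not a rate for people who have already reacted, because the documents do not show whether those trials excluded such people. They are background and do not measure the gap.

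**The case against.** The strongest reply is that nobody would read E 14 literally. It describes one reaction and names the two carriers used in the trial, so *and* can be taken as a list of relevant vaccine types. The protocol uses *and* this way elsewhere: in section 6.7, Category 2 immunosuppressive therapy is defined by a period before vaccination *and* a period after it, and use in either must surely count. That is a fair point about intent. It does not settle the reading, because other exclusions that list alternatives (E 04, E 06, E 07, E 08 and E 09) use *or*.

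The second reply is that screening would catch these people anyway:

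- Section 1.3.2 on precautions before injection: "This includes a review of the subject's prior vaccination history with respect to possible hypersensitivity to the vaccine or similar vaccines".
- Section 5.1.4, Visit 1, before vaccination: "Obtain verbal medical history about the subject".
- Section 5.2.6: "Prior to enrollment, subjects will be assessed for pre-existing conditions and illnesses, both past and ongoing".
- Section 5.2.5, where there is a separate primary physician: "the site should ask this primary physician to verify exclusion criteria relating to previous therapies, such as receipt of blood products or previous vaccines".
- Section 13.4.1, at site initiation: "Emphasis will be placed on inclusion and exclusion criteria".
- Section 5.2.9 lets the investigator or sponsor withdraw a subject over safety concerns.

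These steps lower the risk and are part of why the point is minor. None of them states the eligibility rule. The physician and the site-initiation meeting work from the criteria as worded. Section 5.2.6 also says dates are not recorded for medical history, although E 14 depends on a 10-year window.

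Third, the package insert, the investigator's brochure and the site manuals may clarify the matter. They are not available here, so divergent decisions between sites are a possibility and have not been shown. Fourth, the protocol states an Arthus concern only for tetanus toxoid-containing vaccines, so the documented risk supports the tetanus half of the gap and is silent on diphtheria-only vaccines. Both points stand and limit the size of the concern.

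**Conclusion.** The concern holds as a minor wording error. E 14 as written does not match a design in which each vaccine carries one toxoid, and E 09 does not cover the histories it leaves out. Nothing in the documents suggests a deliberate choice to admit people who reacted to a single-toxoid vaccine.

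The practical effect is probably nil or confined to very few subjects. That is a judgment, since the documents give no frequency to calculate from. It assumes that Arthus-like reactions are rare, as section 1.3.2 says, and that most investigators would take *and* to mean either type. The sample size, power and primary non-inferiority analysis do not change. The Per-Protocol Analysis Set could differ only by the classification of any such subject.

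Confidence is high that the wording leaves the gap. Whether any site would in fact enroll such a person is unknown.

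**What to change.** In E 14, in both section 5.2.5 and the Synopsis, change the *and* between the tetanus and diphtheria vaccine types to *or*. The rest of the criterion, including the 10-year window, can stay.

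The cost is one word in two places, with a negligible effect on recruitment. Planned inclusion ended on 11 November 2020. If enrollment has already closed, the change serves as a written clarification: apply the *or* reading to any reported Arthus-like history when Per-Protocol membership is settled before database lock, and carry the corrected wording into later protocols.
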